**Table 9 Response Criteria**

Target Lesions	Non-Target Lesions	New Lesions	Overall Response	Best Response for this Category Also Requires
CR	CR	No	CR	>4 weeks confirmation
CR	Non-CR/ Non-PD	No	PR	
PR	Non-PD	No	PR	>4 weeks confirmation
SD	Non-PD	No	SD	documented at least once >4 weeks from baseline
PD	Any	Yes or No	PD	
Any	PD*	Yes or No	PD	
Any	Any	Yes	PD	no prior SD, PR or CR

Abbreviations: CR = complete response; PD = progressive disease; PR = partial response; SD = stable disease.

\* In exceptional circumstances, unequivocal progression in non-target lesions may be accepted as disease progression

## **7.2 Evaluation of Safety**

Analyses will be performed for all patients having received at least 1 dose of study drug. Safety parameters commonly used for evaluating investigational systemic anticancer treatments are included as safety endpoints including, but not limited to, the incidence of, causality, and outcome of AEs/ SAEs, and changes in vital signs and laboratory values. Investigators who are qualified physicians will assess adverse events as defined by NCI CTCAE, Version 5.0 (<http://ctep.cancer.gov/reporting/ctc.html>). Any AE that changes NCI CTCAE grade over the course of a given episode will have each change of grade recorded on the AE CRFs/worksheets.

All AEs regardless of NCI CTCAE grade must also be evaluated for seriousness.

## **7.3 Definitions of Adverse Events**

### **7.3.1 Adverse Event**

An AE is defined as any untoward medical occurrence in a subject or clinical investigation subject administered a pharmaceutical product and which does not necessarily have to have a causal relationship with this treatment. An AE can therefore be any unfavorable and unintended sign (including an abnormal laboratory finding, for example), symptom, or disease temporally associated with the use of a medicinal product or protocol-specified procedure, whether or not considered related to the medicinal product or protocol-specified procedure. Any worsening (i.e., any clinically significant adverse change in frequency and/or intensity) of a preexisting condition that is temporally associated with the use of the Merck's product, is also an AE.

Changes resulting from normal growth and development that do not vary significantly in frequency or severity from expected levels are not to be considered adverse events. Examples of this may include, but are not limited to, teething, typical crying in infants and children, and onset of menses or menopause occurring at a physiologically appropriate time.

Merck's product includes any pharmaceutical product, biological product, device, diagnostic agent or protocol-specified procedure, whether investigational (including placebo or active comparator medication) or marketed, manufactured by, licensed by, provided by or distributed by Merck for human use.

Adverse events may occur during the course of the use of Merck product in clinical trials, or as prescribed in clinical practice, from overdose (whether accidental or intentional), from abuse and from withdrawal.

Progression of the cancer under trial is not considered an AE.

### 7.3.2 Adverse reaction

An adverse reaction is defined as any AE caused by the use of a drug. Adverse reactions are a subset of all suspected adverse reactions for which there is reason to conclude that the drug caused the event.

### 7.3.3 Suspected Adverse Reaction

A suspected adverse reaction is defined as any AE for which there is a reasonable possibility that the drug caused the AE. For the purposes of IND safety reporting, "reasonable possibility" indicates that there is evidence to suggest a causal relationship between the drug and the AE. A suspected adverse reaction implies a lesser degree of certainty about causality than an adverse reaction.

#### 7.3.3.1 Unexpected

An AE or suspected adverse reaction is considered *unexpected* if it is not listed in the IB or package insert(s), or is not listed at the specificity or severity that has been observed, or, if an IB is not required or available, is not consistent with the risk information described in the general investigational plan or elsewhere in the current application.

"Unexpected," as used in this definition, also refers to AEs or suspected adverse reactions that are mentioned in the IB as occurring with a class of drugs or as anticipated from the pharmacological properties of the drug, but are not specifically mentioned as occurring with the particular drug under investigation.

AEs that would be anticipated to occur as part of the disease process are considered *unexpected* for the purposes of reporting because they would not be listed in the IB. For example, a certain number of non-acute deaths in a cancer trial would be anticipated as an outcome of the underlying disease, but such deaths would generally not be listed as a suspected adverse reaction in the IB.

Some AEs are listed in the IB as occurring with the same class of drugs, or as anticipated from the pharmacological properties of the drug, even though they have not been observed with the drug under investigation. Such events would be considered *unexpected* until they have been

observed with the drug under investigation. For example, although angioedema is anticipated to occur in some subjects exposed to drugs in the angiotensin-converting enzyme (ACE) inhibitor class and angioedema would be described in the investigator brochure as a class effect, the first case of angioedema observed with the drug under investigation should be considered *unexpected* for reporting purposes.

### 7.3.3.2 Serious

An AE or suspected adverse reaction is considered *serious* if, in the view of either the investigator or sponsor, it results in any of the following outcomes:

- Death;
- Life-threatening (i.e., results in an immediate risk of death);
- Requires inpatient hospitalization or prolongation of existing hospitalization;
- Permanent or significant disability/incapacity;
- Gives rise to a congenital anomaly/birth defect, or cancer, or any experience that suggests a significant hazard, contraindication, side effect, or precaution that may require medical or surgical intervention to prevent one of the outcomes listed above;
- Event occurring in a gene therapy study;
- Event that changes the risk/benefit ratio of a study;
- Any other event the Principal Investigator judges to be serious or which would suggest a significant hazard, contraindication, side effect, or precaution

Important medical events that may not result in death, are life-threatening, or require hospitalization may be considered serious when, based upon appropriate medical judgment, they may jeopardize the subject and may require medical or surgical intervention to prevent one of the outcomes listed in this definition. Examples of such medical events include allergic bronchospasm requiring intensive treatment in an emergency room or at home, blood dyscrasias or convulsions that do not result in subject hospitalization, or the development of drug dependency or drug abuse.

**Note:** In addition to the above criteria, AEs meeting either of the below criteria, although not serious per International Council for Harmonisation (ICH) definition, are reportable to Merck in the same timeframe as SAEs to meet certain local requirements. Therefore, these events are considered serious by Merck for collection purposes.

- Is a new cancer (that is not a condition of the study);
- Is associated with an overdose.

Additionally, if an Investigator who is a qualified physician considers an SAE to be related to Merck's product, and the SAE is brought to the attention of the Investigator at any time following consent through the end of the specified safety follow-up period specified in the paragraph above, or at any time outside of the time period specified in the previous paragraph, also must be reported immediately to the Merck clinical team. All subjects with SAEs must be followed up for outcome.

### 7.3.3.3 Life-threatening

An AE or suspected adverse reaction is considered *life-threatening* if, in the view of either the investigator or Merck, its occurrence places the subject or subject at immediate risk of death. It does not include an AE or suspected adverse reaction that, had it occurred in a more severe form, might have caused death.

### 7.3.4 Definition of an Overdose

For this trial, an overdose of pembrolizumab will be defined as any dose of 1000 mg or greater ( $\geq 5$  times the indicated dose). An overdose of other study treatment will be defined as the administration of a dose that exceeds the dose described in the protocol.

No specific information is available on the treatment of overdose of pembrolizumab. In the event of overdose, the subject should be observed closely for signs of toxicity. In the event of an overdose of any study treatment, appropriate supportive treatment should be provided if clinically indicated.

### 7.3.5 Events of Clinical Interest

Selected non-serious and SAE are also known as ECIs and must be reported to Merck.

For the time period beginning when the ICF is signed until treatment allocation/randomization, any ECI, or follow up to an ECI, that occurs to any patient must be reported within 24 hours to the Merck clinical team if it causes the patient to be excluded from the trial, or is the result of a protocol-specified intervention, including but not limited to washout or discontinuation of usual therapy, diet, placebo treatment or a procedure.

For the time period beginning at treatment allocation through 30 days following cessation of treatment, any ECI, or follow up to an ECI, whether or not related to Merck's product, must be reported within 24 hours to the Merck clinical team, either by electronic media or paper.

Events of clinical interest for this trial include:

1. An overdose of Merck's product, as defined in Section 7.3.4, that is not associated with clinical symptoms or abnormal laboratory results.
2. An elevated AST or ALT lab value that is greater than or equal to  $3 \times$  ULN and an elevated total bilirubin lab value that is greater than or equal to  $2 \times$  ULN and, at the same time, an ALP lab value that is less than  $2 \times$  ULN, as determined by way of protocol-specified laboratory testing or unscheduled laboratory testing.\*

\*Note: These criteria are based upon available regulatory guidance documents. The purpose of the criteria is to specify a threshold of abnormal hepatic tests that may require an additional evaluation for an underlying etiology. The trial site guidance for assessment and follow up of these criteria can be found in the Investigator Trial File Binder (or equivalent).

## 7.4 Recording of an Adverse Event

Refer to the Data Safety Monitoring Plan, located in Appendix 2.

## 7.5 Follow-up of Adverse Events

All AEs will be followed with appropriate medical management until resolved. Subjects removed from study for unacceptable AEs will be followed until resolution or stabilization of the AE. For selected AEs for which administration of the investigational drug was stopped, a re-challenge of the subject with the investigational drug may be conducted if considered both safe and ethical by the Investigator.

## 7.6 Adverse Events Monitoring

Refer to the Data Safety Monitoring Plan, located in Appendix 2.

## 7.7 Expedited Reporting

### Reporting to the Data and Safety Monitoring Committee

If a death occurs during the treatment phase of the study or within 30 days after the last administration of the study drug(s) and it is determined to be related either to the study drug(s) or to a study procedure, the Investigator or his/her designee must notify the DSMC Chair (or qualified alternate) within 1 business day of knowledge of the event. The contact may be made via phone or e-mail.

### Reporting to UCSF Institutional Review Board

The UCSF PI must report events to the UCSF IRB according to institutional guidelines.

UCSF IRB website for guidance in reporting adverse events: <https://irb.ucsf.edu/adverse-event>

### Expedited Reporting to the Food and Drug Administration

If the study is being conducted under an IND, the Sponsor (or the Sponsor-Investigator) is responsible for determining whether or not the suspected adverse reaction meets the criteria for expedited reporting in accordance with federal regulations (21 CFR §312.32).

The Sponsor (or Sponsor-Investigator) must report in an IND safety report any suspected adverse reaction that is both serious and unexpected. The Sponsor needs to ensure that the event meets all three definitions:

- **Suspected adverse reaction**
- **Unexpected**
- **Serious**

If the adverse event does not meet all three of the definitions, it should not be submitted as an expedited IND safety report.

The timeline for submitting an IND safety report to FDA is no later than **15 calendar days** after the Investigator determines that the suspected adverse reaction qualifies for reporting (21 CFR 312.32(c)(1)).

Any unexpected fatal or life-threatening suspected adverse reaction will be reported to FDA no later than **7 calendar days** after the Investigator's initial receipt of the information (21 CFR 312.32(c)(2)).

Any relevant additional information that pertains to a previously submitted IND safety report will be submitted to FDA as a Follow-up IND Safety Report without delay, as soon as the information is available (21 CFR 312.32(d)(2)).

### **Reporting to Merck**

See section 7.8.

## **7.8 Reporting Events to Merck**

All AEs, SAEs and other reportable safety events that occur after the ICF is signed but before treatment allocation must be reported by the investigator if the subject is receiving placebo run-in or other run-in treatment, if the event causes the subject to be excluded from the study, or is the result of a protocol-specified intervention, including but not limited to washout or discontinuation of usual therapy, diet, or a procedure.

- All AEs from the time of treatment allocation through 30 days following cessation of study treatment must be reported by the investigator.
- All AEs meeting serious criteria, from the time of treatment allocation/randomization through 90 days following cessation of study treatment, or 30 days following cessation of study treatment if the subject initiates new anticancer therapy, whichever is earlier, must be reported by the investigator.
- All pregnancies and exposure during breastfeeding, from the time of treatment allocation/randomization through 120 days following cessation of study treatment, or 30 days following cessation of study treatment if the subject initiates new anticancer therapy, must be reported by the investigator.
- Additionally, any SAE brought to the attention of an investigator at any time outside of the time period specified above must be reported immediately to the Merck clinical team if the event is considered to be drug related.

Investigators are not obligated to actively seek AE or SAE or other reportable safety events in former study subjects. However, if the investigator learns of any SAE, including a death, at any time after a subject has been discharged from the study, and he/she considers the event to be reasonably related to the study treatment or study participation, the investigator must promptly notify the Merck clinical team.

All initial and follow-up AEs, SAEs and other reportable safety events will be recorded and reported to the Merck clinical team or designee within the timeframes as indicated in Table 10.

**Table 10 Reporting Time Periods and Timeframes for Adverse Events and Other Reportable Safety Events**

Type of Event	Reporting Time Period:  Consent to Randomization/ Allocation	Reporting Time Period:  Randomization/ Allocation through Protocol-Specified Follow-up Period	Reporting Time Period:  After the Protocol Specified Follow-up Period	Timeframe to Report Event and Follow-up Information to Merck a :
Serious Adverse Event (SAE)	Report if: - due to protocol-specified intervention - causes exclusion - subject is receiving placebo run-in or other run-in treatment	Report all	Report if: - drug/vaccine related. (Follow ongoing to outcome.)	Within 24 hours of learning of event
Non-Serious Adverse Event (NSAE)	Report if: - due to protocol-specified intervention - causes exclusion - subject is receiving placebo run-in or other run-in treatment	Report all	Not required	Per data entry guidelines
Overdose	Report if: - receiving placebo run-in or other run-in medication	Report all	Not required	Within 5 days of learning of event
Event of Clinical Interest (require regulatory reporting)	Report if: - due to intervention - causes exclusion	Report - Potential DILI - Require regulatory reporting	Not required	Within 24 hours of learning of event
Event of Clinical Interest (Do not require regulatory reporting)	Report if: - due to intervention - causes exclusion	Report - non-DILI ECIs and those not requiring regulatory reporting	Not required	Within 5 days of learning of event

Type of Event	Reporting Time Period:  Consent to Randomization/ Allocation	Reporting Time Period:  Randomization/ Allocation through Protocol-Specified Follow-up Period	Reporting Time Period:  After the Protocol Specified Follow-up Period	Timeframe to Report Event and Follow-up Information to Merck a :
Cancer	Report if: - due to intervention - causes exclusion	Report all	Not required	Within 5 days of learning of event
Pregnancy/Lactation Exposure	Report if: - due to intervention - causes exclusion	Report all	Previously reported – Follow to completion/termination; report outcome	Within 24 hours of learning of event
a. SAE reports and any other relevant safety information are to be forwarded to the Merck Global Safety [contact].				

### 7.8.1 Reporting of Pregnancy and Lactation

Although pregnancy and infant exposure during breastfeeding are not considered AEs, any pregnancy or infant exposure during breastfeeding in a subject (spontaneously reported to the investigator or their designee) that occurs during the trial is reportable to the Merck clinical team.

All reported pregnancies must be followed to the completion/termination of the pregnancy. Pregnancy outcomes of spontaneous abortion, missed abortion, benign hydatidiform mole, blighted ovum, fetal death, intrauterine death, miscarriage and stillbirth must be reported as serious events (Important Medical Events). If the pregnancy continues to term, the outcome (health of infant) must also be reported.

Such events must be reported within 24 hours to the Merck clinical team by either electronic media or paper. Electronic reporting procedures can be found in the EDC data entry guidelines. Paper reporting procedures can be found in the Investigator Trial File Binder (or equivalent).

### 7.8.2 Protocol-Specific Exceptions to Serious Adverse Event Reporting

Efficacy endpoints as outlined in this section will not be reported to the Merck clinical team. See Table 10 for events that are reportable to Merck.

Specifically, the suspected/actual events covered in this exception include any event that is disease progression of the cancer under study.

The investigator will monitor unblinded aggregated efficacy endpoint events and safety data to ensure the safety of the patients in the trial. Any suspected endpoint which upon review is not progression of the cancer under study will be forwarded to Merck as an SAE within 24 hours of determination that the event is not progression of the cancer under study.

## 8 Statistical Considerations and Evaluation of Results

### 8.1 Study Endpoints

**Primary endpoint:** The proportion of subjects with  $\geq 2$ -fold increase in the number of T1ICs between baseline and CN/MET specimens.

#### Secondary endpoints:

- The clinical efficacy of preoperative pembrolizumab-based therapy in subjects with advanced RCC will be assessed by ORR, defined as CR or PR by RECIST 1.1 criteria.
- The clinical efficacy of:
  - Continued pembrolizumab-based therapy will be assessed as follows:
    - In subjects who achieve CR or PR/SD followed by R0 resection: proportion of subjects who remain disease-free at the end of the 1 year continued treatment period (1-year DFS rate), and at 1 year following the end of the continued treatment period (2-year DFS rate), and the median DFS.
    - In subjects who achieve PR/SD with residual disease following CN/MET: proportion of subjects who remain progression-free at the end of the 1 year continued treatment period (1-year PFS rate) and at 1 year following the end of the continued treatment period (2-year PFS rate), and the median PFS.
  - Safety will be assessed and reported using NCI CTCAE version 5.0.
    - Surgical complications using Clavien-Dindo classification (Appendix 3)

#### Exploratory endpoints

- The relationship between clinical efficacy (by above measures) and changes in T1ICs (by above measures) will be explored.
- Clinical efficacy: pathologic response rate, R0 resection rate
- The changes in frequency and numbers of circulating T cells will be assessed by flow cytometry.
- Comprehensive assessment will be performed to explore the tumor microenvironment, including for PD-L1 status. Transcriptional profiling of tumor microenvironment

constituents (including T cell subsets, tumor, and stroma) in pre- and post-treatment specimens will be analyzed .

- Changes in the T cell repertoire will be explored via high resolution TCR sequencing, in both blood and tumor specimens.
- Molecular profiling of pre- and post-treatment tumor and normal tissue will be performed to explore biomarkers of response. Neoepitope burden will be assessed.
- Wilcoxon rank-sum test will be used to assess whether there is a relationship between any of the immune cell subsets and objective radiographic response as well as pathologic response. Cox-proportional hazard models will be applied to assess if there is relationship between any of the immune cell subsets and PFS. Parallel analysis will be performed for PD-L1 expression. Wilcoxon rank-sum test will also be used to assess whether the T cell receptor clonality diversity index is different between responders vs. non-responders (defined by objective radiographic response or pathologic response), and between subjects who have progression within 1-year vs. those whose disease has not progressed. Additional analyses of immunocorrelative data are detailed in the procedures manual.

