## 1 Introduction

### 1.1 Background on Indication

It is estimated that there are more than 60,000 new cases of kidney cancer and over 14,000 deaths due to kidney cancer in the US each year[1], with the majority of cases being renal cell carcinoma (RCC). Tyrosine kinase inhibitors (TKIs) and allosteric mammalian target of rapamycin (mTOR) inhibitors have been the standard of care for subjects with advanced RCC for the past decade. Approved agents for advanced RCC in this class include axitinib in the second-line setting, which showed a progression free survival (PFS) benefit versus sorafenib in a randomized phase III trial [2], lenvatinib in combination with everolimus after one prior line of anti-angiogenic therapy, which demonstrated PFS and overall survival (OS) benefit over everolimus alone in an open-label phase II study [3], and more recently cabozantinib both after at least one line of anti-angiogenic therapy, where it showed an OS benefit over everolimus [4], and also in the first line, where it showed a PFS benefit versus sunitinib for intermediate- and poor-risk disease [5]. Unfortunately, approximately 20% of subjects never experience clinically significant benefit, and treatment-related resistance eventually emerges in the remainder of subjects [2-4]. Median overall survival (OS) for subjects with metastatic RCC (mRCC) is estimated to be approximately 22 months [5] in the TKI era.

More recently, checkpoint inhibitors have become standard of care treatments in this disease. Immunotherapy has long demonstrated its role in the treatment of RCC, including the experience with high-dose interleukin-2 (IL-2) [6]. The current era of immunotherapy with programmed cell death 1 (PD-1) and PD-1 ligand 1 (PD-L1) directed antibodies promises even greater rewards. Nivolumab (Opdivo®, Bristol Myers Squibb) received regulatory approval in the second line-setting in 2015, demonstrating survival benefit compared to everolimus in subjects who are refractory to previous TKI therapy in the CheckMate 025 study [[7]. Pembrolizumab as monotherapy has also demonstrated activity for previously untreated, advanced clear cell RCC; however, with a confirmed objective response rate of 34% [12], this is a population of patients in whom further therapeutic advances can be made.

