### 1.2.2.1 Axitinib and Pembrolizumab

A notable result that was recently reported was the combination of axitinib with pembrolizumab versus sunitinib in an open-label phase III trial for patients with treatment-naïve advanced RCC [18]. The estimated percentage of patients alive at 12 months was significantly higher with axitinib + pembrolizumab (89.9% versus 78.3%, HR 0.53), as was median PFS (15.1 versus 11.1 months, HR 0.69), with an objective response rate of 59% with axitinib + pembrolizumab. Grade 3 or higher adverse events of any cause were seen in 76% of patients receiving axitinib + pembrolizumab, with 63% of patients experiencing a Grade 3 or higher adverse event attributed to the combination therapy. Most frequent treatment-related adverse events ( $\geq$ Grade 3) were hypertension (21%), elevations in alanine aminotransferase (12%), diarrhea (7%), and elevations in aspartate aminotransferase (7%). Adverse events regardless of attribution led to discontinuation of either drug (31%), discontinuation of both drugs (11%), interruption of either drug (70%), and dose reduction of axitinib (20%).

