### Immune-related Gene Expression Profile (GEP)

Intratumoral expression levels of select genes will be analyzed using an analytically validated platform. Association between the immune-related GEP and response to pembrolizumab has been established using these genes in melanoma and in cancers from clinical studies KN012 (head and neck, bladder, and gastric cancers) and KN028 (ovarian, esophageal, and other cancers). Data from these cohorts has been used to derive a GEP, which combines the expression levels of several key genes into a single scalar score [40]. The pattern of association in the esophageal cohort of KN028 using a prototype GEP suggested the ability to identify patients who may not respond to pembrolizumab by identifying tumors that have low values of the GEP. The GEP includes genes from immune-regulatory pathways and a GEP score will be tested for association with response to pembrolizumab in retrospective fashion. The relationship between GEP and the probability of response will be used to develop cut-offs that may have high clinical utility.

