### 3.2 Number of Subjects

Up to 84 subjects in total will be enrolled. Up to twelve subjects will be accrued into Cohort A, with the first 6 subjects undergoing a safety lead-in to evaluate the safety of pembrolizumab monotherapy and potential surgical complications as assessed per the Clavien-Dindo classification (Appendix 3). After six (6) subjects have been enrolled into Cohort A, up to 36 evaluable subjects will be accrued concurrently to each pembrolizumab-based combination cohort, based on group sequential design. See section 8.2.1 for details regarding sample size determination.

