### 8.1.2 Randomization

This is a non-randomized study. Cohorts will be accrued concurrently.

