### 8.1.3 Stratification Factors

There are no planned stratification factors.

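### The exploratory biomarker tests in Section 8.1 carry no cohort term, so if cohorts are pooled, a drug effect on an on-treatment marker can look like an association with response

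*Combined protocol and SAP*

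**What the plan says.** The last bullet of Section 8.1, Exploratory endpoints, sets out the tests. For response, a "Wilcoxon rank-sum test will be used to assess whether there is a relationship between any of the immune cell subsets and objective radiographic response" and also pathologic response. For time to event, "Cox-proportional hazard models will be applied to assess if there is relationship between any of the immune cell subsets and PFS". PD-L1 is to be analysed in parallel. TCR clonality is compared by rank-sum test between responders and non-responders, and between subjects with and without progression within one year. No cohort stratum, cohort covariate or restriction to one cohort is given. Further immunocorrelative analyses are referred to a procedures manual, which is not among the documents reviewed.

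On the design, Section 8.1.2 says "This is a non-randomized study. Cohorts will be accrued concurrently", and Section 8.1.3 says "There are no planned stratification factors". Section 3.2 says "Up to 84 subjects in total will be enrolled": up to 12 in Cohort A and up to 36 in each combination cohort. Section 8.2.1 lowers the latter to 30 if there is no dose reduction. Cohort A receives pembrolizumab alone, Cohort B adds axitinib, and Cohort C adds an agent not yet chosen.

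On the gene expression profile (GEP), Section 1.4.2 says that the score's relationship with the probability of response "will be used to develop cut-offs that may have high clinical utility". It names no data set, hold-out sample or correction.

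**The concern.** A pooled responder versus non-responder comparison mixes two things: whether the marker goes with response among subjects on the same drugs, and whether the two groups contain different shares of each cohort. If response is more frequent in Cohort B, responders are more often Cohort B subjects. Any marker that axitinib raises or lowers will then differ between responders and non-responders, even if it carries no information about who responds within a cohort.

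This applies most directly to on-treatment and change-from-baseline measures, such as immune-cell changes and post-treatment profiling. The primary objective itself supposes that treatment may alter these cells. Section 2.1.3.2 lists the search for potentially predictive biomarkers as an objective, and the study rationale is to understand response and resistance. A pharmacodynamic effect of the added drug reported as a marker of response would work against that purpose.

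**Working it through.** **No figure to reproduce.** The plan gives no alpha, sample size, number of subsets or power for these tests, so the check is a simulation under stated assumptions.

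**Inputs from the documents**
- Cohort sizes: 12 in A (Section 3.2) and 30 in B (Section 8.2.1, no dose reduction).
- Response rates: monotherapy "with a confirmed objective response rate of 34" percent (Section 1.1), and the phase III trial "with an objective response rate of 59% with axitinib + pembrolizumab" (Section 1.2.2.1). For the range, the phase Ib rate for this combination is 73% (Section 1.1). All three are results of outside studies, used here as assumptions.

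**Inputs assumed**
- Nominal two-sided 5%.
- A marker independent of response within each cohort, shifted by 0 to 2 SD in the combination cohort(s).
- All subjects evaluable; 6,000 runs per setting. Monte Carlo standard error near 5% is √(0.05 × 0.95 / 6,000) ≈ 0.28 percentage points.

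**Step 1: how large an artefact to expect.**
- Responders: A 12 × 0.34 = 4.08, B 30 × 0.59 = 17.70. Share from B = 17.70 / 21.78 = 81.3%.
- Non-responders: A 7.92, B 12.30. Share from B = 12.30 / 20.22 = 60.8%.
- Expected marker difference = (0.813 − 0.608) × shift ≈ 0.20 × shift. A 1 SD drug effect becomes a spurious difference of about 0.20 SD, and a 2 SD effect about 0.41 SD.
- With equal response rates the two shares are equal and the difference is zero.

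**Step 2: the two tests.** The pooled test is the ordinary rank-sum test on all subjects. The van Elteren test ranks within cohort. Let W_h be the rank sum of the m_h responders among the n_h subjects of cohort h. Without ties,

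z = Σ[W_h − m_h(n_h + 1)/2]/(n_h + 1) ÷ √{Σ m_h(n_h − m_h)/[12(n_h + 1)]}.

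A shift common to a whole cohort leaves the within-cohort ranks, and so z, unchanged.

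**Step 3: false-positive rates, 12 + 30 subjects, 34% versus 59%**

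| Cohort shift (SD) | Pooled | Stratified |
|---|---|---|
| 0 | 5.3% | 5.2% |
| 0.5 | 5.9% | 4.8% |
| 1 | 9.0% | 4.7% |
| 1.5 | 12.9% | 5.2% |
| 2 | 14.8% | 4.3% |

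**Step 4: sensitivity of the pooled test**

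| Setting | 1 SD | 2 SD |
|---|---|---|
| 12 + 36, 34% vs 59% | 8.7% | 15.5% |
| 12 + 36 + 36, Cohort C like B | 6.8% | 13.1% |
| 12 + 30, 34% vs 73% | 16.0% | 33.9% |
| 12 + 36, equal response rates | 4.8% | 5.1% |

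The stratified test lay between 3.8% and 5.2% in every setting run. The Cox models were not simulated. The same mechanism applies to them if PFS differs by cohort, but I put no size on it.

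**The case against.** **Pooling is not stated.** The design is organised by cohort: sample size, interim decisions and primary completion are all per cohort. Run within cohorts, the same tests carry no cohort confounding. This stands as far as it goes. But Section 8 says so explicitly where it means each combination cohort, and the matching objective in Section 2.1.3.2 covers all treated subjects. Pooling is therefore the more natural reading, and under either reading a sentence is needed.

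**Section 8.1.3 is a design statement.** It follows the item on randomization and is not worded as a rule for the biomarker tests. That is right. The point rests on the absence of a cohort term in Section 8.1 itself.

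**The response rates are not projections for this trial.** They come from outside studies, whereas preoperative response here is assessed after 9 weeks. This stands, and Step 4 shows that the effect disappears when the rates are equal.

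**Baseline markers are outside the mechanism.** Axitinib cannot shift a pre-treatment PD-L1 or TCR measurement. A baseline difference would need selective assignment to cohorts, which I have not quantified. For PD-L1, Section 1.4.2 also frames the question among subjects on combined checkpoint and VEGF inhibition, which would leave out Cohort A. Both limits stand.

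**On GEP, a reader might infer that the plan will pick the best-looking cut-off on this trial's data and test it on the same data.** The documents do not say this. The GEP text sits in a list of investigations that may be done, names no data set, and plans no p-value for a selected cut-off; the score itself came from other studies. As illustration only, with a useless score, 48 subjects and a 59% response rate, the best-looking cut-off over the middle 80% of values reaches p<0.05 in 39% of simulated trials, against 5.5% for a median split. That describes a procedure the plan does not specify.

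**Conclusion.** The point holds in a conditional form. Section 8.1 specifies tests without a cohort term for cohorts on different drugs. If they are pooled, an on-treatment marker shifted by the added drug can show a false association with response. At the assumed 34% and 59%, the false-positive rate rises from 5% to about 6% to 15% per test over shifts of 0.5 to 2 SD. Three things are needed together: pooling, unequal response rates, and a marker that differs by cohort.

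A reader might go further and conclude that cohort differences will be reported as predictive markers. The documents do not support that: pooling is unstated, the response rates are background figures, the shifts are my assumption, and at moderate shifts the inflation is modest. The GEP remark is secondary and applies only if cut-offs are developed on this trial's own responses.

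No primary or secondary endpoint depends on these tests, and the procedures manual was not available. I rate this a low-priority improvement.

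**What to change.** In Section 8.1, Exploratory endpoints:
- Replace the plain rank-sum tests with the van Elteren test, with cohort as the stratum.
- Stratify the Cox models by cohort.
- Show per-cohort results beside the combined estimate, and state the cohorts included for each marker, PD-L1 in particular.

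In Section 1.4.2, state which data will be used for GEP cut-offs. If they are this trial's own responses, fix the cut-off in advance (for example at the median), or report cross-validated response rates and label the cut-off hypothesis-generating.

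The cost is a few sentences of plan text and standard code, with no new subjects, samples or visits. Stratifying gives up the between-cohort comparison and so a little power. With about four responders expected among 12 subjects in Cohort A, that cohort's own result will be imprecise and should be presented as such.
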